
4.2 RATIONALE

4.2.1 Study design

DRI11772 study will consist of the evaluation of the efficacy and safety of 2 dose levels/regimens of SAR156597 administered subcutaneously over a 52-week treatment period and, the determination of the optimal dose level/regimen for the treatment of patients with IPF.

It will be a multinational, randomized, double-blind, placebo-controlled, 3-parallel group study conducted in out-patients suffering from IPF according to the American Thoracic Society/ European Respiratory Society/ Japanese Respiratory Society/ Latin American Thoracic Association (ATS/ERS/JRS/ALAT) guideline criteria and confirmed by a multidisciplinary panel of experts in IPF.

Patients who discontinue treatment during the study will be followed for the full planned 52 week duration of the study in order to ensure the collection of efficacy outcomes on all randomized patients and minimize the potential for bias in analyses due to missing data.

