### **1.3 DETERMINATION OF SAMPLE SIZE**

Approximately 300 patients will be randomized in this study, 100 per treatment arm. Based on the enrollment in prior studies of this population approximately half of the patients are expected to be older than 65.

The sample size calculations are based on the primary efficacy variable of % predicted FVC change from baseline to week 52, with the following assumptions:

- A common standard deviation of 12% is assumed based on the data from previous trials (26)
- A 5% mean difference between each dose and placebo in change from baseline in % predicted FVC
- A 2-sided 5% significance level with 80% power

Ninety two (92) patients per treatment arm will yield 80% power to detect a 5 percentage point difference between the treatment groups and placebo. Additional patients will be randomized in each regimen to allow for dropouts; therefore, approximately 100 patients will be randomized into each treatment arm, for a total sample size of approximately 300 patients for the study.

[figure not shown]
As a rank-based method will be used for analysis the actual power may differ from these calculations, however, calculations based on the ASCEND study (28), which used the same analysis method and endpoint confirm that the planned analysis should have at least 80% power. No adjustment is made for multiplicity since a hierarchical testing procedure is proposed.

Calculations were made using nQuery Advisor 7.0.

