			in efficacy analysis provided that the endpoint was measured or could be calculated (e.g. at least 1 baseline and 1 post-baseline values for imputing and calculating a change).
NA	NA	Baseline definition has been revised because the timeslot between a screening and a baseline value is large (up to 4 weeks) and there will not be several assessments at 52 weeks.	Last available value before first IMP administration.
NA	NA	%predicted DLCO analysis is of interest, it was missing in protocol.	Addition of the %predicted DLCO exploratory endpoint analysis.
NA	NA	
Primary efficacy endpoint - change in week 52 missing data (due to death or lung-transplant) imputation approach: the time-to-death or lung transplant approach is more sensitive in ranking patients. For example, a patient who dies early will be more penalized than a patient who dies lately during the study.
 
Primary efficacy endpoint - change in week 52 missing data (due to reasons other death or lung-transplant) imputation approach:
 
 
patients taking treatment at 52 weeks will be imputed using a linear regression run on their treatment arm completers.
 
patients not taking treatment at 52 weeks will be imputed using a linear regression run on the placebo completers.
 
	
Time-to-death or lung transplants will be used instead of allocating the lowest rank for all died and lung transplanted patients.
 
For patients with a week 52 missing data (due to reasons other than death or lung transplant), depending on treatment intake at 52 weeks, a linear regression will be performed on a particular set of completers.

NA	NA	Disease progression endpoint - change in analysis cut-off date: Day 375 will be used instead of superior boundary of week 52 analysis window (Day 406) in order to prevent from non-random censures.	Patients not meeting the definition for disease progression will be considered censored at the time of their week 52 FVC or DLCO assessment provided that it was performed before Day 375. For patients with a missing week 52 assessment, the censoring time will be the time of the last measured FVC or DLCO assessment. For patients with week 52 assessment performed after Day 375, the censoring time will be Day 375.

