### 2.4.4.1 Analysis of primary efficacy endpoint(s)

The primary efficacy endpoint will be analyzed on the mITT population. In the primary analysis, assessments at week 52 will be used regardless of whether the patient has previously discontinued treatment.

Due to the non-normality of the endpoint distribution, the absolute change from baseline in % predicted FVC at week 52 as defined in [Section 2.1.3.1](#) will be analyzed in the mITT population using a rank ANCOVA model adjusted on the stratification factor (with/without background therapy). This model will use the ranks of absolute change from baseline to week 52 in % predicted FVC as the outcome and the ranks of baseline % predicted FVC as a covariate. In case of ties, the mean of the corresponding ranks will be assigned.

To summarize, the following steps will be performed:

A) On the pool of arms SAR156597 200mg qw and placebo:

1. Imputation of missing data at 52 weeks

a) Week 52 missing values due to reasons other than death or lung transplant

- i. Patients in active arm and taking treatment at 52 weeks: Missing values at 52 weeks will be imputed using a model estimated from the subset of patients in the active arm who completed the 52-week treatment period and with a week 52 value. The imputation model will be based on a Mixed Model with Repeated Measures (MMRM) with fixed categorical effect of stratification factor (with/without Background Therapy) and repeated categorical effect for time point (baseline, week 12, week 24, week 36, week 52). Parameters will be estimated with the Newton-Raphson algorithm, an unstructured covariance matrix will model the within-patient errors, and the denominator degrees of freedom will be estimated using Satterthwaite's approximation. Missing values at 52 weeks will be imputed using the empirical best linear unbiased prediction (EBLUP).

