- ii. Other patients (patients in active arm and not taking treatment at 52 weeks; or patients in placebo arm): Missing values at 52 weeks will be imputed using a model estimated from the subset of patients in the placebo arm who completed the 52-week treatment period and with a week 52 value. The imputation model will be based on a Mixed Model with Repeated Measures (MMRM) with fixed categorical effect of stratification factor (with/without Background Therapy) and repeated categorical effect for time point (baseline, week 12, week 24, week 36, week 52). Parameters will be estimated with the Newton-Raphson algorithm, an unstructured covariance matrix will model the within-patient errors, and the denominator degrees of freedom will be estimated using

- Satterthwaite's approximation. Missing values at 52 weeks will be imputed using the empirical best linear unbiased prediction (EBLUP).
- iii. When running the imputation model, if the predicted absolute change from baseline calculated from the predicted week 52 value is greater than zero (increases above baseline), it will be set to zero.
  - iv. The non-monotone missing patterns with a week 52 value available will not be imputed.
- b) Week 52 missing values due to lung transplant:
    - i. Any % predicted FVC value assessed after a lung transplant will be considered as missing.
    - ii. No imputation of a week 52 value for % predicted FVC. In step 2, patients will be ranked worse than missing data due to reasons other than death or lung transplant.
  - c) Week 52 missing values due to death :
    - i. No imputation of a week 52 value for % predicted FVC. In step 2, patients will be ranked worse than missing data due to lung transplant.
2. Rank ANCOVA
- a) Ranking within each stratum of the stratification factor (with/without Background Therapy)
    - i. Death: Missing data due to death will be ranked based on a time-to-death, with shortest time until death as the worst (lowest) rank (from 1 to  $n_{\text{stratum,death}}$ ).
    - ii. Lung transplant: Missing data due to lung transplant will be ranked based on a time-to-lung transplant, with shortest time until lung transplant as the worst (lowest) rank (from  $n_{\text{stratum,death}}+1$  to  $n_{\text{stratum,death}}+n_{\text{stratum,lungtransplant}}$ ). So, missing data due to lung transplant will be less penalized than deaths.

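### The model that imputes missing Week 52 FVC is fitted only to placebo patients who completed treatment, so patients lost after stopping are likely imputed too favourably if they stop because they are declining

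*SAP*

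**What the plan says.** The primary analysis does not depend on staying on treatment: "assessments at week 52 will be used regardless of whether the patient has previously discontinued treatment" (SAP 2.4.4.1). The protocol supports this. "Patients who discontinue treatment during the study will be followed for the full planned 52 week duration of the study" (Protocol 4.2.1), and Protocol 10.3.4 asks stoppers to attend the scheduled visits for FVC and DLCO where possible.

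For Week 52 values missing for reasons other than death or transplant, step A.1.a.ii of SAP 2.4.4.1 covers active patients not on treatment at Week 52 and all placebo patients. Their value is the EBLUP from "a model estimated from the subset of patients in the placebo arm who completed the 52-week treatment period and with a week 52 value". The model is an MMRM over baseline and Weeks 12, 24, 36 and 52 with an unstructured covariance. Step A.1.a.iii sets any predicted gain over baseline to zero. Deaths and transplants are not imputed; they take the lowest ranks. Step B repeats the procedure for the q2w arm.

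Table 1 in SAP 1.5 summarises the rule more loosely: "patients not taking treatment at 52 weeks will be imputed using a linear regression run on the placebo completers". It calls the model a linear regression and gives no reason for the restriction to completers. Protocol 11.4.2.1 had instead used a regression on all available FVC measurements.

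**The concern.** The patients to be imputed are mostly people who stopped treatment and then did not return. Those most like them are placebo patients who stopped and did return, and this group is left out of the fit. A model fitted to people who stayed on treatment learns how FVC evolves among those who stayed. If falling FVC makes stopping more likely, the fitting set has lost steep decliners, and its predictions for stoppers run high.

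The restriction is not needed technically. A likelihood-based MMRM with unstructured covariance accepts incomplete records and off-treatment values.

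The imputed changes go straight into the ranks of the primary test. If more active than placebo patients are lost off treatment, the comparison would lean towards the active arm.

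**Working it through.** **1. The plan's own figures, for scale.** SAP 1.3 assumes a difference of 5 points, an SD of 12, a two-sided 5% level and 80% power.

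- n = 2 × (1.960 + 0.842)² × 12² / 5² = 90.4, so 91 per arm by the normal approximation.
- By the t test, power is 0.798 at 91 and 0.803 at 92, so 92 reproduces.
- 92 / 100 implies an 8% allowance for dropout.
- The SE of a difference in means at 100 per arm is 12 × √(2/100) = 1.70 points.

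**2. Who informs the model in step A.1.a.ii.**

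| Patient | Value used in the primary test | In the fit? |
|---|---|---|
| Placebo, completed treatment, Week 52 present (even with a missed interim visit) | observed | yes |
| Placebo, stopped, returned at Week 52 | observed | no |
| Placebo, Week 52 missing | imputed from this fit | no |
| Active, off treatment, Week 52 missing | imputed from this fit | no |

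Off-treatment values are therefore absent from the fitting only. A patient's own earlier values still inform the EBLUP, and no text excludes off-treatment ones.

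**3. Bias per imputed patient.** The documents give no stopping rate, return rate or off-treatment decline, so these are assumptions. The simulations used random slopes with a mean decline of 4 or 6 points a year, slope SD 8 or 11, measurement SD 3, roughly 19 to 35% stopping and half of stoppers returning. The model was given correct visit means and an unstructured covariance. A positive figure means too favourable, in points of % predicted FVC.

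| Stopping depends on | Completers fit, no cap | Completers fit, cap | All-placebo fit, cap |
|---|---|---|---|
| measured FVC only | +0.4 to +0.8 | +0.1 to +0.5 | −0.1 to −0.4 |
| measured FVC and current decline | – | +1.8 to +5.7 | +1.0 to +3.3 |

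In the second row the all-placebo fit cuts the bias by 1 − 1.0/1.8 = 44% at the low end and 1 − 3.3/5.7 = 42% at the high end, or roughly 40 to 50% overall.

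**4. From patient to treatment difference.** Both arms' off-treatment losses use the same model. If the bias b is the same in both arms, the mean difference moves by (share imputed in active − share imputed in placebo) × b.

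| Imputed, active vs placebo | b = 0.1 to 0.5 | b = 1.8 to 5.7 |
|---|---|---|
| 8% vs 8% | 0 | 0 |
| 12% vs 4% | 0.01 to 0.04 | 0.14 to 0.46 |
| 20% vs 10% | 0.01 to 0.05 | 0.18 to 0.57 |

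The largest entry, 0.57, is 11% of the 5-point target and a third of the SE (0.57 / 1.70 = 0.34).

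**5. The rank test itself.** This was a simplified one-stratum simulation with 2,000 runs, 100 per arm, a true on-treatment effect of 5 points, stopping at Week 24, half of stoppers returning, and the cap applied. Here g is how much worse stoppers do than the model predicts, before the cap. Full data means that no Week 52 value is missing.

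| Imputed, active vs placebo | g | Estimate, plan / full data | Power, plan / full data |
|---|---|---|---|
| 8% vs 8% | 5 | 4.52 / 4.52 | 0.79 / 0.76 |
| 12% vs 4% | 0 | 4.20 / 4.31 | 0.74 / 0.74 |
| 12% vs 4% | 5 | 3.80 / 3.50 | 0.63 / 0.54 |
| 20% vs 10% | 0 | 3.74 / 3.88 | 0.65 / 0.64 |
| 20% vs 10% | 5 | 3.23 / 2.88 | 0.51 / 0.37 |

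With g = 5 and unequal losses, the plan overstates the estimate by 0.30 to 0.35 points. With g = 0 and unequal losses, the cap makes it slightly unfavourable to active.

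**The case against.** The strongest reply is that the plan already guards against over-favourable imputation.

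- **The cap.** It pulls imputed values down. If stopping depends only on measured FVC, it removes most of the bias and makes an all-placebo fit slightly too pessimistic. Another simulation under similar assumptions put the capped completers fit at −0.32 to +0.26 and the capped all-placebo fit at −0.25 to −0.88. This stands: under that mechanism neither fit is clearly better.
- **Cancellation.** Placebo losses get the same model, so equal losses leave the difference almost unchanged. This also stands.
- **Worst outcomes.** Deaths and transplants take the lowest ranks and lie outside this imputation. True, but it leaves patients who decline, stop and are lost.
- **Sensitivity 1.** It is not restricted to completers: placebo withdrawals are handled under MAR and active ones by copy increment from reference. However, it replaces the rank test by an MMRM with multiple imputation and treats deaths and transplants differently, so a changed result could not be traced to the fitting set. Sensitivity 2 uses on-treatment data only, and no delta or tipping-point analysis is planned.

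A reader might infer that the plan throws away off-treatment FVC. It does not: observed off-treatment Week 52 values are analysed. Nor are all partly observed patients dropped from the fit, because a placebo completer with a missed interim visit stays in it.

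**Conclusion.** The point holds as a weakness in the choice of fitting set. It is not a demonstrated bias in favour of the drug. The text of step A.1.a.ii is clear, and the restriction is unexplained and unnecessary for the method used. A favourable direction is likely if patients stop because they are declining, but no figure in the documents establishes it.

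The size depends mainly on why patients stop: small if measured FVC explains it, several points per imputed patient if current unmeasured decline also drives it. A shift in the comparison also needs unequal off-treatment losses. Even then it stays near half a point or less in the mean difference for the loss rates tried, although the simulated loss of power shows that this can matter near the significance boundary.

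A reader might also infer that the data already collected would fully correct the problem. They would not: under informative stopping, more than half of the bias remains after the change. This is a cheap improvement, not a flaw that invalidates the primary analysis.

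**What to change.** In SAP 2.4.4.1, step A.1.a.ii, estimate the imputation model from all valid % predicted FVC values of placebo patients in the mITT population before death or transplant, on or off treatment. Drop the conditions of completed treatment and an available Week 52 value. Keep the cap and the ranking of deaths and transplants as they are.

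Align the Table 1 entry in SAP 1.5 with this, including its description of the model as a linear regression, and give the reason for the choice. Keep the completers-only fit, with the same rank test, as a sensitivity analysis so that the effect of this one choice can be seen. Because some bias may remain, a delta analysis on off-treatment losses would be a useful complement.

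The cost is a few lines of SAP text and one selection condition in the program, with no new data. In simulation at 100 patients, the sampling SD of the imputation hardly changed (2.6 against 2.7). The downside is that imputed values become somewhat less favourable and, with the cap, may be slightly conservative.

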## 1.6 STATISTICAL MODIFICATIONS MADE IN THE STATISTICAL ANALYSIS PLAN

Not applicable.

## 2 STATISTICAL AND ANALYTICAL PROCEDURES

### 2.1 ANALYSIS ENDPOINTS

#### 2.1.1 Demographic and baseline characteristics

The baseline value is defined as the last available value obtained before or equal to the date and time of the first double-blind Investigation Medicinal Product (IMP) administration. For patients randomized and not treated, the baseline value is defined as the last available value obtained before or equal to the date and time of randomization.

All baseline safety and efficacy parameters are presented along with the on-treatment summary statistics in the safety and efficacy sections ([Section 2.4.4](#) and [Section 2.4.5](#)).

#### *Demographic characteristics*

Demographic variables at baseline are gender (Male, Female), race (Caucasian/White, Black, Asian/Oriental, Other), age in years (quantitative and qualitative variable: <40, ≥40 and >65, ≥65 and <75, ≥75 years), ethnicity (Hispanic/Latino, Not Hispanic/Latino).

#### *Medical or surgical history*

Medical (or surgical) history includes (but are not limited to) the following previous relevant medical and surgery history collected at baseline:

- All prior significant medical conditions, and/or hospitalization history: eg. pneumonia, asthma, Chronic Obstructive Pulmonary Disease (COPD), diabetes, hypertension, pulmonary arterial hypertension, congestive heart failure, esophageal reflux, depression, sleep apnea, myocardial infarction or arrhythmias, need for major surgery or surgical complications.

#### *Habits*

Habits includes:

- smoking habits (never smoke, quit smoking (have smoked regularly in their lifetimes but have stopped at least 8 days ago), currently smokes (smoked at least 1 cigarette, as a mean, per day during the past 7 days)), pack years (if currently smoking or quit smoking: One pack year is smoking 20 cigarettes a day for one year), mean smoking duration for quit and current smokers in years.
- alcohol habits (frequency of alcoholic drinks in the last 12 months (Never/At least monthly/At least weekly/At least daily/Occasionally), number of standard drinks (1 or 2/Greater than 2 where standard drink means 1 pint/bottle of beer, 1 glass of wine, 1 shot of hard liquor...) per day when drinking alcohol)

### ***Disease characteristics at baseline***

Specific disease history includes:

- IPF diagnosis algorithm: Identifiable Causes of Interstitial Lung Disease (ILD) (yes, no), Diagnosis confirmation by Central review (yes, no), IPF diagnosis based on HRCT alone OR HRCT and Surgical Lung biopsy
- HRCT UIP (usual interstitial pneumonitis) determination during adjudication (Definite UIP, Probable UIP, Possible UIP and Definitely not UIP)
- Lung Biopsy UIP determination during adjudication (Definite UIP, Probable UIP, Possible UIP and Definitely not UIP)
- Time since diagnosis of IPF (in years and by category: <1, 1-≤3 and >3 years)
- Time since first symptoms of IPF (years)
- Any acute exacerbation within the past 12 months before enrollment (yes, no) and if yes, time from most recent date of acute exacerbation (months and by category (<6 months and ≥6 months))
- Family IPF history (yes, no, unknown)
- Oxygen therapy need (yes, no) and if yes number of hours the patient is on supplemental oxygen therapy per day
- Currently taking pirfenidone or nintedanib for at least 12 weeks prior to enrollment (yes, no) and if yes, will continue with pirfenidone or nintedanib during the study (yes, no)

The following efficacy parameters will be also summarized at baseline (see definition in [Section 2.1.3](#)):

- FVC (forced vital capacity): L and % predicted (quantitative and by tercile (≤60, >60 and ≤75, >75)),
- FEV1 (forced expiratory volume in 1 second): L and % predicted,
- FEV1/FVC ratio,
- % predicted DLCO (diffusing capacity of the lung for carbon monoxide): quantitative and by tercile (≤40, >40 and ≤55, >55),
- residual volume (RV): L,
- total lung capacity (TLC): L,
- SpO2 (peripheral oxygen saturation): % under oxygenotherapy and under ambient air,
- SGRQ total score,
- EQ-5D-5L total score,
- 6MWT (6-meter walking test) distance (m),
- Total Fibrosing ILD score.

### ***Other baseline characteristics***

Other baseline characteristics include stratification factor (With/Without Background Therapy) as per IVRS/IWRS and e-CRF (patients taking at least a dose or part of a dose of Nintedanib or Pirfenidone at randomization (Visit 2/Day 1) will be considered in the With Background Therapy stratum).

Any technical details related to computation, dates and imputation for missing dates are described in [Section 2.5](#).

#### **2.1.2 Prior or concomitant medications**

All medications taken before randomization and until the end of the study are to be reported in one of the specific case report form pages:

- Pirfenidone or Nintedanib (within 12 weeks prior to randomization (baseline) and during the course of the study) on the dedicated page using ATC code,
- Systemic Corticosteroids category will gather the routes described in [Appendix C](#) (within 4 weeks prior to randomization (baseline) and during the course of the study).
- Other prior and concomitant specific medications (within 30 days before randomization (baseline) and during the course of the study) on the dedicated page:
  - In particular, N-acetylcysteine (administered at the dosage recommended by Czech Republic guidelines) will be selected using a WHO-DD codelist.
  - Anti-acids will be selected using a WHO-DD codelist.
    - in particular, H2 receptor blocker will be selected using a WHO-DD codelist
    - proton pump inhibitors (PPI) will be selected using a WHO-DD codelist.

All medications will be coded using the World Health Organization-Drug Dictionary (WHO-DD) using the version currently in effect at Sanofi at the time of database lock. All WHO-DD codelists used in this study are detailed in [Appendix F](#).

- Prior medications are those the patient used from 12 weeks prior screening up to first investigational medicinal product (IMP) intake. Prior medications can be discontinued before first administration or can be ongoing during treatment phase.
- Concomitant medications are any treatments received by the patient concomitantly to the IMPs, from first IMP administration to the last IMP administration + 84 days. A given medication can be classified both as a prior medication and as a concomitant medication. Concomitant medications do not include medications started during the post-treatment period (as defined in [Section 2.1.4](#)).
- Post-treatment medications are those the patient took in the period running from the day after the last IMP administration + 84 days period (ie, 85 days after the day of last dose of double-blind IMP injection).

Any technical details related to computation, dates, imputation for missing dates are described in [Section 2.5](#).

